3.6.3 Follow-Up Visits — Survival/Post-Disease Progression

Once a subject experiences confirmed disease progression or starts a new anti-cancer therapy, the subject moves into the survival follow-up phase and should be contacted (e.g., phone, email, etc.; in-person visit not required) at least every 6 months (± 4 weeks) to collect information on new anti-cancer treatments received and to assess for survival status until death, withdrawal of consent, or the end of the study, whichever occurs first (see Study Calendar)

Abbreviated Title: IL-15+Mogamulizumab
Version Date: 11/16/2020

3.7 STUDY CALENDAR

Procedure	Screening	Baseline	Study Cycles						Disease Evaluations	End of Treatment and Disease Progression	Post-Treatment Follow-Up		
			C1			C2-6					Safety ¹	Follow-Up (Prior to PD)	Survival (Post-PD)
Scheduling Window (Days):	-28 to -1 ²		-14 ³	8 (-3)	15 (-3)	22 (-3)	1 (-3)	15 (-3)	Every 8 weeks ⁴	Treatment discon/PD ⁵	Day 30 (±7)	Every 60 or 90 days ⁶	Every 6 months ⁷
Confirmation of Diagnosis ⁸	X												
Physical Exam and ECOG PS ⁹	X	X		X	X	X	X	X		X	X	X	
CBC with Differential	X	X	X	X	X	X	X	X		X	X	X	
Reticulocyte Count	X	X	X	X	X	X	X	X		X	X	X	
Chemistry Panels ¹⁰ , LDH	X	X	X	X	X	X	X	X		X	X	X	
Serum Lipase and Amylase		X	X	X	X	X	X	X		X	X	X	
Uric Acid, Total Protein		X	X	X	X	X	X	X					
PT/INR and aPTT	X	X	X				X			X	X	X	
Thyroid Function (i.e., TSH, T4)	X	X	X				X			X	X	X	
Urinalysis	X	X	X				X			X			
Pregnancy Test (urine/serum; WOCBP)	X	X	X										
Hepatitis B and C, HIV Antibody, HTLV-1/2	X												
HLA typing (A, B, C, DR, DQ)		X	X										
Anti-nuclear antibody (ANA), rheumatoid factor (RF) and anti-thyroid antibody	X	X											
Clonal T-cell receptor rearrangement by PCR	X												
Iron panels, Folate, and B12, C-reactive Protein, IL-2Ra		X	X										
Creatine phosphokinase (CPK), troponin	X	X	X							X		X	

Abbreviated Title: IL-15+Mogamulizumab
Version Date: 11/16/2020

Procedure	Screening	Baseline	Study Cycles						Disease Evaluations	End of Treatment and Disease Progression	Post-Treatment Follow-Up		
			C1			C2-6					Safety ¹	Follow-Up (Prior to PD)	Survival (Post-PD)
Scheduling Window (Days):	-28 to -1 ²		-14 ³	8 (-3)	15 (-3)	22 (-3)	1 (-3)	15 (-3)	Every 8 weeks ⁴	Treatment discon/PD ⁵	Day 30 (+7)	Every 60 or 90 days ⁶	Every 6 months ⁷
Pulmonary function tests (PFTs) ¹¹	X												
T, B, NK cell subsets		X		X	X		X	X		X	X	X	
Imaging studies ¹²	X	X							X	X		X	
MRI, Lumbar Puncture ¹³		X							X	X		X	
Bone Marrow Aspiration/Biopsy ¹⁴		X								X	X		
Flow Cytometry ¹⁵		X							X	X	X	X	
Clinical photography and dermatology assessment/ global score ¹⁶		X							X	X		X	
Radiologic Evaluation/ tumor measurement ¹⁷		X							X	X		X	
EKG, TTE	X												
Symptoms/Adverse Events Assessment, Concomitant Medication Review	X	X					X			X	X	X	
Research Blood/Tissue Samples ¹⁸		X	Refer to Section 5.1										
Survival Status													X

NOTE: Any other tests should be performed as clinically indicated. See Section 3.2 for drug administration information. See Section 5.1 for information on research blood samples/correlative studies to be collected.

Abbreviated Title: IL-15+Mogamulizumab
Version Date: 11/16/2020

¹ 30 days (+7) following last dose, and 90 days (+14) after last dose of mogamulizumab (via clinic or phone). If initiating new anti-cancer therapy within 30 days after last dose of mogamulizumab, 30-day safety follow-up visit must occur before first dose of new therapy.

² Screening and Baseline evaluations should be performed within 28 days prior to enrollment and dosing, respectively, unless otherwise noted and with the following exceptions: Confirmation of diagnosis (no time limit); HIV antibody, HTLV-1/2 serologies, Hepatitis B surface antigen and Hepatitis C antibody, EKG, and bone marrow aspiration/biopsy (all within 3 months) **NOTE:** Any screening tests performed within the specified time frame for baseline do not need to be repeated.

³ Within 14 days prior to dosing on C1D1, with the following exceptions: Pregnancy test (within 7 days of dosing; must be negative).

⁴ \pm 2 days. Confirmatory scans should also be obtained 4 weeks following initial documentation of objective response.

⁵ To be done at end of treatment (30 days after last dose of study treatment; may be combined with 30 day safety follow-up, if timing coincides). If subject to initiate new anti-cancer therapy assessments should occur before the first dose of the new therapy.

⁶ Follow-up to occur about every 60 days (\pm 7 days) for first 6 months, every 90 days (\pm 14 days) for 2 years, then every 6 months (\pm 28 days) for another 2 years and then annually (\pm 6 weeks) until disease progression or initiation of new anti-cancer therapy.

⁷ After disease progression or initiation of new anti-cancer therapy, contact for survival about 6 months (\pm 4 weeks).

⁸ Pathologic review/confirmation of diagnosis by Laboratory of Pathology, NCI (no time limit). If archival sample is not available, a fresh tumor biopsy and/or peripheral blood sample will be obtained.

⁹ Physical exams to include medical history (i.e., complete at Screening/Baseline; interim on study and in follow-up), vitals, weight, and height (screening only).

¹⁰ Chemistry panels include: Acute care, Hepatic, and Mineral.

¹¹ Diffusing capacity/alveolar volume (DLCO/VA), forced expiratory volume in 1 second (FEV1) for patients with significant pulmonary or smoking history.

¹² At screening a CT scans of neck, chest, abdomen, and pelvis should be performed (with IV and PO contrast, unless patient is allergic or has renal insufficiency; other imaging may be substituted at the discretion of the investigator). Other body areas may be imaged if clinically indicated. MRI of the brain is only required in patients with suspected involvement of CNS. At screening, a FDG-PET/CT torso (extremities to be included if there is confirmed or suspected disease involvement). At baseline one or more of the following studies: CT, MRI, FDG-PET/ CT and or clinical photography. FDG/ PETs to be done between C3 and C4 and at EOT.

¹³ Patients with neurological symptoms or signs should undergo MRI scan of the brain and lumbar puncture

¹⁴ Baseline bone marrow aspiration/ biopsy with flow cytometry must be done within 3 months prior to starting treatment. During post-treatment follow-up, repeat bone marrow aspiration/ biopsy needed only to confirm a CR.

¹⁵ Peripheral blood flow cytometry may be done for disease evaluation of patients who had circulating leukemic cells detected at baseline, and for patients with CTCL regardless of their baseline results.

¹⁶ To be performed in selected patients with cutaneous disease (as determined by PI or AI).

¹⁷ Dermatology assessment and Global/mSWAT scoring will be used instead of or in addition to radiologic evaluation for patients with predominantly cutaneous disease

¹⁸ Samples for correlative research are to be collected as indicated in Section 5.1. Prior biopsy specimen blocks will be used for CCR4 staining if available. If archival tissue is not available or adequate, baseline punch biopsy of the skin or core needle biopsy of a lymph node/visceral lesion is required, otherwise this is optional.

Abbreviated Title: IL-15+Mogamulizumab

Version Date: 11/16/2020

3.8 COSTS AND COMPENSATION

3.8.1 Costs

NIH does not bill health insurance companies or participants for any research or related clinical care that participants receive at the NIH Clinical Center. If some tests and procedures performed outside the NIH Clinical Center, participants may have to pay for these costs if they are not covered by insurance company. Medicines that are not part of the study treatment will not be provided or paid for by the NIH Clinical Center.

3.8.2 Compensation

No direct compensation will be provided on the study.

3.8.3 Reimbursement

On this study, the NCI will cover the cost for some of the expenses. Some of the costs may be paid directly by the NIH and some may be reimbursed to the subject. Someone will work with subjects to provide more information.

3.9 CRITERIA FOR REMOVAL FROM PROTOCOL THERAPY AND OFF STUDY CRITERIA

Prior to removal from study, effort must be made to have all patients complete a safety visit approximately 30 days following the last dose of study therapy. Additional safety visits and follow-up will continue as per Section **3.6**.

3.9.1 Criteria for removal from protocol therapy

Patients who meet the following criteria should be discontinued from protocol therapy:

- Completion of protocol therapy (i.e., up to 6 cycles)
- Confirmed disease progression
- Intercurrent illness that prevents further administration of treatment
- Unacceptable toxicities as listed in Section **3.1.1** or those toxicities listed in Section **3.3** that require treatment to be stopped.
- Subject's request to withdraw from protocol therapy
- Investigator's decision to withdraw the patient
- Subject's non-compliance with trial treatment or procedure requirements that requires removal in the opinion of the PI
- Pregnancy
- The drug manufacturer can no longer provide the study agent
- Study is cancelled for any reason
- Failure to maintain eligibility prior to starting treatment

3.9.2 Off-Study Criteria

- Subject requests to be withdrawn from study
- Subject is lost to follow-up*
- Death

- Study is cancelled for any reason

3.9.3 Lost to Follow-up

* A participant will be considered lost to follow-up if he or she fails to return for two consecutive scheduled visits and is unable to be contacted by the study site staff.

The following actions must be taken if a participant fails to return to the clinic for a required study visit:

- The site will attempt to contact the participant within 3 business days to reschedule the missed visit, and counsel the participant on the importance of maintaining the assigned visit schedule and ascertain if the participant wishes to and/or should continue in the study.
- Before a participant is deemed lost to follow-up, the investigator or designee will make every effort to regain contact with the participant (where possible, 3 telephone calls and, if necessary, a certified letter to the participant's last known mailing address or local equivalent methods). These contact attempts should be documented in the participant's medical record or study file.
- Should the participant continue to be unreachable, he or she will be considered to have withdrawn from the study with a primary reason of lost to follow-up.

4 CONCOMITANT MEDICATIONS/MEASURES

Medications or vaccinations specifically prohibited in the exclusion criteria are not allowed during the ongoing trial with the exception of oral or parenteral steroids if they are administered more than 7 days before the start of or more than 7 days after the end of IL-15 infusion. If there is a clinical indication for a prohibited medication/ measure during the trial, discontinuation from trial therapy may be required.

For premedication and supportive care measures, see Sections [3.2.1](#), [3.2.2](#), and [3.2.3](#).

4.1 ACCEPTABLE MEDICATIONS

All treatments that the investigator considers necessary for a subject's welfare may be administered at the discretion of the investigator in keeping with the community standards of medical care. All concomitant medication will be recorded on the case report form (CRF) including all prescription, over-the-counter (OTC), herbal supplements, and IV medications (not to include continuous intravenous fluids). If changes occur during the trial period, documentation of drug dosage, frequency, route, and date may also be included on the CRF.

All concomitant medications received within 28 days before the first dose of trial treatment and 30 days after the last dose of trial treatment should be recorded.

Patients who are deemed to be at high risk for CNS involvement by the primary investigator and who have not received intrathecal prophylaxis prior to enrollment may receive it as clinically indicated after completion of the first cycle of therapy. Patients who have evidence of CNS involvement with lymphoma by flow cytometry and have no parenchymal lesions on brain imaging may receive intrathecal treatment as clinically indicated after completion of the first cycle of therapy.

Abbreviated Title: IL-15+Mogamulizumab

Version Date: 11/16/2020

4.2 PROHIBITED MEDICATIONS

Patients are prohibited from receiving the following therapies during treatment on this trial:

- Other therapy for the disease under study not specified in this protocol, unless specifically noted as permitted
- Investigational agents other than rhIL-15 and mogamulizumab
- Radiation therapy

NOTE: Radiation therapy to a symptomatic solitary lesion may be allowed at the investigator's discretion.

- Live vaccines within 30 days prior to the first dose of trial treatment and while participating in the trial. Examples of live vaccines include, but are not limited to, the following: measles, mumps, rubella, varicella/zoster, yellow fever, rabies, BCG, typhoid vaccine and FluMist.

Patients who, in the assessment by the investigator, require the use of any of the aforementioned treatments for clinical management should be removed from the study treatment. Patients may receive other medications that the investigator deems to be medically necessary.

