3.6 POST-TREATMENT EVALUATIONS

Post treatment evaluations (i.e., End of Treatment Visit) will be performed approximately 30 days after the last dose of protocol treatment. If a subject initiates a new anti-cancer therapy within 30 days after the last dose of trial treatment, the 30-day safety follow-up visit must occur before the first dose of the new therapy. If the patient cannot return to the Clinical Center for this visit, a request will be made to have a local physician or laboratory collect a CBC with differential and send the results. If this is not possible, patients may be assessed by telephone for symptoms.

Unless otherwise noted, follow-up will occur at the following time point: every 60 days (\pm 7 days) for 6 months; then every 90 days (\pm 14 days) for 2 years; then every six months (\pm 28 days) for 2 years, then annually (\pm 6 weeks) at the discretion of the investigator. Any other evaluations and tests should be performed as clinically indicated.

Upon disease progression or initiation of other anti-cancer therapy, contact will be for survival only until the subject is off study (i.e., every 3 months [\pm 4 weeks]); unless otherwise clinically indicated. See Study Calendar (Section [3.7](#)) for additional information. Any adverse events which are present at the time of discontinuation should be followed in accordance with the safety requirements.

Patients who stop treatment early will be followed until completion of the Safety Follow-up Visit or until death, whichever occurs first. Patients removed from study treatment for unacceptable adverse event(s) will be followed until resolution or stabilization of the adverse event.

Abbreviated Title: IL-15+Mogamulizumab

Version Date: 11/16/2020

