3.6.2 Follow-Up Visits — Prior to Disease Progression

Patients who complete trial treatment without evidence of disease progression will move into the Follow-up Phase and may be assessed every 60 days (± 7 days) for 6 months; then every 90 days (± 14 days) for 2 years; then every six months (± 28 days) for 2 years, then annually (± 6 weeks) after finishing treatment by radiologic imaging or other clinical assessments to monitor disease status. Every effort should be made to collect information regarding disease status until the start of new anti-neoplastic therapy, or disease progression. If the patient cannot return to the Clinical Center for any of these visits, a request will be made to have a local physician or laboratory collect a CBC with differential and send the results. If this is not possible, patients may be assessed by telephone or email for symptoms.

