6.3.2 Response Criteria for MF/SS

Global Response (GR) score (**APPENDIX C**) will be used for assessing response in patients with CTCL ([41](#)). GR score incorporates separate responses in each component of the TNBM staging (i.e., skin, nodes, viscera and blood; **APPENDIX C**). No patient with a global OR should have less than a PR in the skin.

Abbreviated Title: IL-15+Mogamulizumab

Version Date: 11/16/2020

The mSWAT ([19](#)) is an instrument utilized to track the skin tumor burden in MF/SS. It measures the percentage total body-surface area (TBSA, %) involvement separately for patches, plaques, and tumors within 12 body regions using the patient's palm and fingers representing 1% of TBSA. Patients with erythroderma are assessed for percentage of TBSA involved with patches and/or plaques. The percentage of TBSA for each lesion type is multiplied by a number (patch = 1, plaque = 2; tumor = 4) and summed to derive the mSWAT score. The mSWAT for each patient will be determined by the same individual at all study visits.

A complete response (CR) requires 100% clearing of skin disease and a partial response (PR) requires $\geq 50\%$ reduction in the mSWAT score compared with baseline. CR/PR requires confirmation by repeat assessment after ≥ 4 weeks. Stable disease is defined as less than 50% reduction to less than 25% increase in the mSWAT score compared with baseline. PD is defined as $\geq 25\%$ increase in the mSWAT score from baseline or $\geq 50\%$ increase in the sum of the products of the greatest diameters of pathologically positive lymph nodes compared with baseline.

Time to response is the time from the first treatment dose until the patient first meets the criteria for a 50% decrease in the GR score. The duration of response (DOR) is the time from first CR/PR until the GR score is increased from nadir to more than 50% of the difference between the baseline and nadir scores. Time to progression (TTP) is the time from start of treatment until PD. If patients goes off treatment for any purpose, this date is used for determination of TTP and/or DOR.

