6.3.3 Response Criteria for ATLL

Table 12: Response Criteria for Adult T-cell Leukemia-Lymphoma

Response	Definition	Lymph nodes	Extranodal masses	Spleen, liver	Skin	Peripheral blood	Bone marrow
CR*	Disappearance of all disease	Normal	Normal	Normal	Normal	Normal †	Normal
CRu*	Stable residual mass in bulky lesion	$\geq 75\%$ decrease ‡	$\geq 75\%$ decrease ‡	Normal	Normal	Normal †	Normal
PR*	Regression of disease	$\geq 50\%$ decrease ‡	$\geq 50\%$ decrease ‡	No increase	$\geq 50\%$ decrease	$\geq 50\%$ decrease	Irrelevant
SD*	Failure to attain CR/PR and no PD	No change in size	No change in size	No change in size	No change in size	No change	No change

Abbreviated Title: IL-15+Mogamulizumab

Version Date: 11/16/2020

RD/PD	New or increased lesions	New or $\geq 50\%$ increase §	New or $\geq 50\%$ increase §	New or $\geq 50\%$ increase	$\geq 50\%$ increase	New or $\geq 50\%$ increase	Reappearance
Not assessable							
CR: complete response, CRu: unconfirmed complete response, PR: partial response, SD: stable disease, RD/PD: relapsed disease/progressive disease *Require each criterion to be present for a period of at least 4 weeks. † Provided that $<5\%$ of flower cells remained, complete remission will be judged to have been attained if the absolute lymphocyte count, including flower cells is $< 4 \times 10^9/L$. ‡ Calculated by the sum of the products of the greatest diameters of measurable disease. § Defined by $\geq 50\%$ increase from nadir in the sum of the products of measurable disease. Defined by $\geq 50\%$ increase from nadir in the count of flower cells and an absolute lymphocyte count, including flower cells, of $> 4 \times 10^9/L$.							

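### Radiation allowed on treatment under Section 4.2 has no cut-off in the response rules, so a CR or PR produced by radiation would count in ORR as a drug response

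*Combined protocol and SAP*

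**What the plan says.** **Radiation.** Section 4.2 lists radiation therapy among the prohibited treatments and qualifies it with a NOTE: "Radiation therapy to a symptomatic solitary lesion may be allowed at the investigator's discretion". It closes by saying that patients who, in the investigator's assessment, "require the use of any of the aforementioned treatments for clinical management should be removed from the study treatment". That sentence does not mention the NOTE.

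**Response.** Section 6.3.4 takes the best response recorded between the start of treatment and progression or recurrence. For MF/SS, Section 6.3.2 and Appendix C define a skin PR as a fall of at least 50% in mSWAT from baseline, and "CR/PR requires confirmation by repeat assessment" after at least 4 weeks. For ATLL, Table 12 in Section 6.3.3 uses the sum of products of measurable disease for nodes and extranodal masses, and requires each criterion to hold for at least 4 weeks. None of these places says what happens to a lesion that has been irradiated.

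**Time-to-event endpoints.** Section 6.3.6 ends PFS at relapse, progression or death. Section 6.3.8 counts alternative lymphoma therapy as an EFS event and names radiation as an example. Section 6.3.2 adds: "If patients goes off treatment for any purpose, this date is used for determination of TTP and/or DOR".

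**Follow-up.** Section 3.6 states: "Upon disease progression or initiation of other anti-cancer therapy, contact will be for survival only until the subject is off study". Section 3.6.2 asks for disease status only up to new therapy or progression, and under Section 3.6.3 a subject who "starts a new anti-cancer therapy, the subject moves into the survival follow-up phase".

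**The concern.** Radiation is an effective local treatment for these lymphomas, and the protocol treats it as anti-lymphoma therapy when it defines EFS. If it is given to a patient who stays on the study drugs, later assessments mix its effect with the drug effect. The study is single-arm, open-label and investigator-assessed, so nothing downstream would separate the two. ORR heads the list of secondary endpoints in Section 10.1, and Section 10.4.7 also reports it by diagnosis and CCR4 status, where one patient weighs more. At stake is whether a response in the ORR numerator can be attributed to rhIL-15 plus mogamulizumab.

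**Working it through.** The plan gives no figure on this point to reproduce. The check follows an irradiated patient through the rules and then sizes one case.

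**Step 1. The two readings of Section 4.2.**

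- *The closing sentence governs.* The patient is removed from treatment. Sections 3.6 to 3.6.3 arguably stop disease assessment at the start of other anti-cancer therapy, and the off-treatment date is used for TTP and DOR in MF/SS. Little of the gap remains.
- *The NOTE governs as an exception.* The patient stays on treatment. The off-treatment rule is not triggered, and the follow-up rules concern the post-treatment phase. Section 6.3.4 keeps accepting assessments until progression. Sections 6.3.2, 6.3.3 and Appendix C exclude no irradiated lesion, and Sections 10.3 and 10.4 add no cut-off. A CR or PR first met after radiation counts.

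**Step 2. Effect of one case on ORR.** Inputs: 12 patients at the MTD and a maximum of 18 evaluable patients (Section 10.2); 95% Agresti-Coull interval (Section 10.4.1). Assumption for illustration: ORR near one third without the case.

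Formula: ñ = n + z², p̃ = (x + z²/2)/ñ, interval p̃ ± z√(p̃(1 − p̃)/ñ), with z = 1.96.

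| n | Without the case | With the case | Shift |
|---|---|---|---|
| 12 | 4/12 = 33.3% (13.6 to 61.2%) | 5/12 = 41.7% (19.3 to 68.1%) | 1/12 = 8.3 points |
| 18 | 6/18 = 33.3% (16.1 to 56.4%) | 7/18 = 38.9% (20.2 to 61.5%) | 1/18 = 5.6 points |

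The intervals overlap over most of their width: 19.3 to 61.2% at n = 12 and 20.2 to 56.4% at n = 18.

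**Step 3. What a false PR requires in skin-only MF/SS.** Let s be the irradiated lesion's share of baseline mSWAT, with the lesion cleared by radiation, and d the fractional fall in untreated disease. The total fall is s + (1 − s)d. A PR needs this to be at least 0.50, so s ≥ (0.5 − d)/(1 − d).

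| d | Smallest s |
|---|---|
| 0 | 50% |
| 0.2 | 0.3/0.8 = 37.5% |
| 0.3 | 0.2/0.7 = 28.6% |
| 0.4 | 0.1/0.6 = 16.7% |

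Tumours carry weight 4 in mSWAT, so one tumour can hold a larger share of the score than of the skin area. The route is therefore a patient who is already improving but short of PR, and it must survive confirmation after at least 4 weeks. When other compartments are involved, Appendix C also requires a CR or PR in at least one of them for a patient with a skin PR, and no PD in any. Table 12 sets its own criterion for each compartment. A false PR is less likely there.

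**The case against.** **Section 4.2 is untidy, not contradictory.** A reader might infer that its two instructions flatly conflict. The section's first bullet already allows for therapy noted as permitted, and the opening of Section 4 says only that discontinuation may be required. Both support reading the NOTE as a specific exception. This stands, but it is the reading under which the patient stays on treatment and the response rules run on.

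**PFS is not defective.** A reader might infer that PFS also needs a radiation rule. Following PFS to relapse, progression or death whatever other therapy is given is a legitimate choice. EFS is a planned secondary endpoint that counts radiation as an event. This stands in full.

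**Masked progression is not established.** Take a baseline mSWAT of 20: a tumour on 1% of body surface (1 × 4 = 4) plus patches on 16% (16 × 1 = 16). If the patches grow by 40%, they score 22.4. Without radiation the total is 26.4 (+32% from baseline, PD). With the tumour cleared it is 22.4 (+12%, not PD). A reader might infer that radiation hides progression. That holds only with the baseline reference of Section 6.3.2 and Appendix C. Section 6.3.4 refers to the smallest measurement since treatment began. If 16 had been recorded after clearance, 22.4 is +40% and exceeds the 25% threshold. In ATLL, nodal and extranodal PD is a new lesion or at least a 50% "increase from nadir in the sum of the products of measurable disease", so radiation that lowers the nadir can bring PD forward.

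**A false PR is remote.** The NOTE covers one symptomatic solitary lesion, and a global response in MF/SS needs at least a skin PR, so irradiating a node alone cannot produce one. This limits how often the problem arises. It does not remove the rule that would count the case.

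**Conclusion.** The point holds for ORR and is minor. With the NOTE read as an exception, Section 6.3.4 and the response criteria would credit to the drugs a CR or PR first reached because of radiation. One case is worth 8.3 points at n = 12 or 5.6 points at n = 18. These sizes assume that a case occurs. The documents do not say how often such radiation would be given, and the lesion shares in Step 3 are constructed illustrations. ORR is secondary and descriptive, and no decision rule depends on it. MTD, DLT, OS and EFS are unaffected. The documents do not support extending the point to a flaw in PFS or to a general claim that progression would be hidden.

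**What to change.** (a) In the closing sentence of Section 4.2, except radiation permitted under the NOTE. If the sponsor does not want irradiated patients to continue, deleting the NOTE would also settle the wording.

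(b) In Sections 6.3.4 and 10.4.3, base the main ORR on assessments made before any radiation to a disease site, so that a CR or PR first met afterwards does not count. Say explicitly how a response seen before radiation but confirmed after it is handled; under this rule it would not count. Report a sensitivity ORR that uses all assessments.

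(c) Leave PFS as defined and report the planned EFS beside it. Add a sensitivity analysis of TTP and DOR that treats the radiation date as the event.

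The cost is a few sentences in an amendment and two short sensitivity analyses. The only extra data item is the radiation date, which EFS already needs. The downside is that an occasional true drug responder who was irradiated is missed in the main ORR, for example when a small lesion was treated and all untreated disease then cleared. The sensitivity ORR makes that patient visible and guards against an estimate that is too low.
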